Appendix 2: Data Safety and Monitoring Plan

Study Oversight:

This study will utilize an institutionally-appointed Data Safety and Monitoring Board (DSMB), which will hold DSMB yearly meetings via teleconference. The DSMB will be responsible for monitoring any data and/or safety issues and also providing recommendations as needed for the following:

- Participant safety
- Initial approval of the protocol and consent forms and subsequent amendments for human subject safety and research ethics
- Data and statistical analysis plan
- Efficacy of the study intervention
- Benefit/risk ratio of procedures and participant burden
- Selection, recruitment, and retention of participants
- Adherence to protocol requirements
- Completeness, quality, and analysis of measurements
- Notification of and referral for abnormal findings

Study Monitoring:

The data to be presented to the DSMB for review will be proposed at the first DSMB meeting and then provided in aggregate at subsequent meetings. At a minimum, recruitment and retention data, baseline characteristics, changes to the protocol and consent or planned analysis, and the following outcome data will be included: asthma medication adherence and asthma-related healthcare utilization. In addition, data quality (timeliness and completeness of data collection, resolution of discrepancies), safety data (adverse events (AEs), serious adverse events (SAEs), and unanticipated problems), and study conduct (protocol deviations) will also be included.

Ongoing monitoring of recruitment will be tracked using a master screening log stored on the study's Way to Health database at the University of Pennsylvania. Way to Health is an NIH-sponsored, web-based platform that automates many of the research functions necessary for conducting randomized controlled trials of behavioral incentives.

Monitoring of data collection will be performed by the research project manager and research assistant:

- Monthly review of adherence data from Way to Health
- Monthly review of EHR data on asthma-related ED visits and hospitalizations

Missing data will be managed by running twice monthly data query reports in the Way to Health database. Data discrepancies will be resolved by the study research assistant and other study staff with corrections and/or comments entered into the Way to Health database within one week of receiving data query.

Protocol deviations will be identified by PI and research project manager and reported to the CHOP IRB through the electronic IRB reporting system in accordance with CHOP IRB policy. These events will be presented to the DSMB and reported to the research team at regularly scheduled study meetings.

Safety Monitoring:

An adverse event (AE) includes any event meeting the following definition:

Any untoward or unfavorable medical occurrence in a human subject, including any abnormal sign (for example, abnormal physical exam or laboratory finding), symptom, or disease, temporally associated with the subject's participation in the research, whether or not considered related to the subject's participation in the research (modified from the definition of adverse events in the 1996 International Conference on Harmonization E-6 Guidelines for Good Clinical Practice).

A Serious Adverse Event (SAE) is defined as any untoward medical occurrence that:

- Results in death
- Is life-threatening
- Results in a persistent or significant disability/incapacity
- Results in in-patient hospitalization or prolongation of existing hospitalization
- Results in a congenital anomaly/birth defect.
- Important medical events that may not result in death, be life threatening, or require hospitalization may be considered a SAE when, based upon medical judgment, they may jeopardize the patient or participant and may require medical or surgical intervention to prevent one of the outcomes listed in this definition.

[figure not shown]
Safety data collection:

Information regarding unanticipated problems and adverse events (AE) and serious adverse events (SAE) will be collected at each study visit through follow-up questionnaires. Once the adverse event has been identified, determined to be unexpected, and at least potentially related to the research study, appropriate CHOP IRB electronic forms will be completed and submitted to the IRB.

Safety data reporting:

Events identified will be recorded and reported to the CHOP IRB. These events will be presented to the DSMB and reported to the research team at regularly scheduled study meetings. Led by the PI, the research team will review each event and make appropriate safety decisions.

SAEs will be communicated by the research personnel immediately to the PI. For SAEs that are determined to be unexpected and at least potentially related to the research study, the study PI will notify the IRB committee assigned to this project at Children's Hospital of Philadelphia, as well as the study DSMB, within 48 hours of first knowledge of the SAE. The IRB and DSMB's assessments of such an event will then be forwarded to the NHLBI within 15 calendar days, as outlined in the "Reportable Events" table below. Because most enrolled patients will have moderate or severe asthma requiring hospitalization in the past, hospitalizations are expected to occur. All AEs (including SAEs) will be followed to their conclusion or stability, with necessary management recorded. Additional details for reporting unanticipated problems, AEs, and SAEs are detailed at the following CHOP Office of Regulatory Affairs website: <https://irb.research.chop.edu/reportable-events> and in accordance with [CHOP IRB SOP 408](#): Unanticipated Problems Involving Risks to Subjects. The flowchart depicted below will be used to make assessments regarding the way the incident will be characterized for reporting.

AEs and unanticipated problems will be summarized in narrative or other format and submitted to the IRB at the time of continuing review. This information will also be reported to NHLBI during the annual progress report. See below for a table which documents the reportable events and when they will be reported to the CHOP IRB, NHLBI, and by whom.

Reportable Event	When Reported to CHOP IRB	When Reported to NHLBI	Reported by Whom
IRB suspension or study termination		3 calendar days from initial receipt of information	CHOP/PI
Study related death or life-threatening event	Within 48 hours of discovery	7 calendar days from initial receipt of information	PI
Unexpected SAE related to study	Within 48 hours of discovery	15 calendar days from initial receipt of information	PI
Unanticipated problems that are not SAEs	7 calendar days	15 calendar days from PI becoming aware of the problem	PI
Serious or continuing non-compliance		10 calendar days	CHOP
AE/SAEs determined not to be related to the study	Annual continuing review	Annual progress report	PI
Minor Protocol deviations (Determined not to be unanticipated problems)	Annual continuing review	Annual progress report	PI

Reproduced from <https://www.nhlbi.nih.gov/research/funding/human-subjects/adverse-event>

Subjects who experience an SAE will be allowed to continue participation in the study. SAE management will be provided by the clinical teams that care for the participants with input from the PI on how medication adherence may have influenced the ED visit or hospitalization.

Risks and Benefits:

Potential risks of trial participation: While the child's usual asthma care may not be minimal risk, risks directly related to study intervention are minimal. There is no risk of discomfort due to the study intervention. The study intervention merely adds electronic monitoring, text message notifications, and nominal financial incentives to already prescribed medications. The main risk is breach of confidentiality. Please refer to the section below on data security and participant confidentiality for the strategies in place to avoid this risk. Upon enrollment, the study team will emphasize to study

[figure not shown]
participants that the trial's activities are not clinical care and that study participants should follow the clinical recommendations and care of their clinical providers. This point is included on the study informed consent form and will be emphasized verbally to all study participants.

Potential benefits of trial participation: Participants in this study may experience improvements in their adherence to their daily controller medications. Improved adherence may lead to better control of asthma and therefore decrease school absences, parental work absences, and the number of visits to the ED or admissions to hospitals.

Risk-benefit assessment: The risks of this study are minimal. The main risk of the study is breach of confidentiality. The potential to improve asthma adherence may improve asthma control and decrease ED visits or hospital admissions for asthma. Therefore, potential benefits of study participation outweigh the potential risks.

Data acquisition, security, and participant confidentiality:

Data will be obtained from participant surveys, the electronic medical record, and the electronic medication adherence sensors placed on the participants' primary asthma controller and rescue medication. For a summary of data entry and transfer, refer to figure below.

Each study subject will be assigned a study ID at the time of enrollment, which will serve as the means of protecting personal health information during data storage. The master list with study IDs will be kept in a separate CHOP network folder from the datasets and will be eliminated after all publication of findings are completed rendering the datasets deidentified.

Epic medical record and study questionnaire data will be entered directly into the Way to Health platform (in the case of patient identifiable information) or on a paper form during the study visits. Electronic adherence data will be transferred electronically from the respiratory sensor platform to the Way to Health Platform via the respiratory sensor platform API (Application Programming Interface). An additional data transfer will be used to extract the analytic data set to the secure CHOP research server for analysis. All databases created will be password-protected and only study team members will have access. All data sets downloaded through the respiratory sensor or Way to Health platforms will be password-protected and stored on the CHOP secured network drive, only accessible to study team members. Please see study protocol section 7.2 for a full description of data security and patient confidentiality measures in place to protect data transfers and storage on the respiratory sensor and Way to Health platforms, CHOP secured network drives, and the transfers between the platforms and drives.

Interim analyses and stopping rules:

Given the minimal risk nature of this study, there are no planned interim analyses or criteria for prematurely stopping the study.

Reporting:

Any change to protocol or amendment to protocol will be approved by CHOP IRB prior to putting in place.

Reports, every year, regarding participant accrual, study progress, AEs and SAEs, and data quality will be developed by the research team. Report by unidentified arms will be made available to the study statistician and the DSMB as specified by the trial protocol, Good Clinical Practices, and applicable regulations. Copies of these reports will be made available to the DSMB and NHLBI by the project biostatistician. Reports to the DSMB and the NHLBI will also include any protocol changes or study conduct issues including protocol deviations.

Conflicts of interest:

The Principal Investigator and co-Investigators have no conflicts of interest. Each year, research team members will be asked to state whether they have developed any new conflicts of interest since the last formal annual report. The research team will report to the DSMB any new potential conflicts of interest prior to each scheduled meeting.

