4.16.2 Efficacy Analysis

We will assess the effectiveness of randomization by comparing the study arm balance on key demographic, clinical, and past health care utilization variables using analysis of variance (ANOVA) and t-tests or the nonparametric equivalent for continuous variables and chi-square tests or Fisher exact tests for categorical variables.

Primary analysis: Our primary outcome will be monthly ICS adherence in months 0-3 (Experiment Phase). Secondary outcomes will include monthly ICS adherence in months 4-6 (Observation Phase), asthma control at the end of the Experiment and Observation period. Secondary outcomes will also include monthly ICS adherence in months 7-13 (follow up period) to assess feasibility and acceptability of longer durations of electronic monitoring. We will consider arcsine transformation on the ICS adherence outcomes as necessary. This technique is commonly used for proportion data. We will use generalized estimating equations (GEE) to adjust for within-subject correlations due to repeated measures for the study's primary and secondary monthly adherence outcomes. Models will include main effects for arm and time (month) and arm-by-month interaction terms to allow for differing ICS adherence over time between arms. The dependent variable of monthly ICS adherence will be defined as mean daily observed-to-prescribed ICS actuation proportion for each study month. Mean daily adherence proportion will be capped at 1, such that participants taking more than their prescribed daily dose cannot receive "extra credit" for doses taken on those days. All statistical tests will be 2-sided. A P-value <0.05 will be considered statistically significant.

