7 STUDY ADMINISTRATION

7.1 Treatment Assignment Methods

7.1.1 Randomization

At the time of enrollment, patients will be assigned to one of three arms using a 2:1:2 block randomization scheme with a block size of 50. Randomization will be accomplished automatically by the Way to Health web-based platform. During the Run-in interval of the study, every caregiver-child dyad will receive electronic ICS use monitoring. Participants for whom we received any adherence monitoring data and at least one text message reply by the end of week 2 will be randomized into one of three experimental conditions at the end of the Run-in period.

Participants will be randomized using block randomization, so arms 1 and 3 will have approximately equal sample sizes and arm 2 will have approximately half the number of

participants(as the study is powered to detect a difference between arms 1 and 3). A total n of 125 will be randomized, with a recruitment goal of about 50 in arms 1 and 3 and 25 in arm 2.

[figure not shown]

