7.1.2 Blinding

Only the PI ([name]) and the statistics team will remain blinded to the assignment of study arm. Neither the subjects nor the study team will be blinded to the study conditions, given that the intervention groups will be receiving incentives and/or reminders (whereas the control group will not) and the study team will provide monthly incentive payments and help facilitate tech support based on the study arm.

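### Coded-arm reports go to a statistician said to be blinded, but 2:1:2 allocation reveals Arm 2 by its size once about 30 to 40 children are randomized

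*Combined protocol and SAP*

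**What the plan says.** Section 7.1.2 (Blinding) states that, together with the PI, "the statistics team will remain blinded to the assignment of study arm". Families and the rest of the study team are not blinded, so this is the only blinding the trial claims. Section 7.2 adds that statisticians can reach only coded data sets on the Way to Health platform.

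Section 7.1.1 allocates "using a 2:1:2 block randomization scheme with a block size of 50", with planned arm sizes of about 50, 25 and 50.

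Appendix 2 deals with reporting in two places:

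- Under Reporting: "Reports, every year, regarding participant accrual, study progress, AEs and SAEs, and data quality will be developed by the research team". It continues: "Report by unidentified arms will be made available to the study statistician and the DSMB as specified by the trial protocol". Then: "Copies of these reports will be made available to the DSMB and NHLBI by the project biostatistician".
- Under Study Monitoring, the minimum data for the DSMB include adherence and asthma-related healthcare use. The data to be shown "will be proposed at the first DSMB meeting and then provided in aggregate at subsequent meetings".

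Appendix 2 also says that no interim analysis or stopping criterion is planned.

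**The concern.** A report split by coded arm goes to a role described as blinded. Coding protects that role only if nothing in the table gives an arm away. Here one arm is planned at half the size of the other two, so its denominator can identify it. If the primary outcome is tabulated too, the two large arms may be told apart by their adherence.

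What is at stake is the freedom left in the analysis:

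- On the primary outcome, section 4.16.2 says: "We will consider arcsine transformation on the ICS adherence outcomes as necessary".
- The primary window is months 1-3 in section 4.14 and months 0-3 in section 4.16.2.
- For the trajectory analysis, sections 4.16.2 and 4.18 leave open the number of groups (up to six, or for example 2 to 5), the polynomial order, and a multinomial or an ordered model.

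A statistician who knows the arms could settle these knowing which way each choice moves the result. Blinding of the statistics team is meant to prevent that.

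**Working it through.** **Inputs from the plan.** Ratio 2:1:2 and block size 50 (7.1.1); adherence 65% in Arm 1 and 35% in Arm 3, 80% power, significance level 0.05, about 20% loss (4.17); two-sided tests (4.16.2).

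**Assumptions.** The plan gives no SD for adherence, so a range of 0.25 to 0.48 is used. Every randomized child is taken to contribute adherence data; fewer would weaken the results in steps 3 and 4.

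**1. The plan's own figure.** Two proportions, two-sided, unpooled variance:

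n = (1.960 + 0.842)² × (0.65×0.35 + 0.35×0.65) / 0.30² = 39.7, so 40 per arm.

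For 20% loss, 40/0.80 = 50, and 50 + 25 + 50 = 125. The sample size reproduces.

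**2. Arm 2 from denominators alone.** A block of 50 holds 20/10/20. Partway through a block, the arm counts follow a multivariate hypergeometric distribution. The exact probability that Arm 2 is strictly the smallest arm is:

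| Randomized | 10 | 20 | 25 | 30 | 40 or more |
|---|---|---|---|---|---|
| Probability | 0.60 | 0.84 | 0.91 | 0.97 | 1.00 (rounded) |

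The figure at 40 can be checked by hand. Ten places are unfilled, so each large arm has at least 20 − 10 = 10 children and Arm 2 has at most 10. Arm 2 can only tie, and only if all ten unfilled places belong to one large arm: 2 × C(20,10)/C(50,10) = 369,512/10,272,278,170, or about 0.00004.

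**3. Arms 1 and 3, only if adherence is shown by coded arm.** The probability that the observed means fall in the planned order is Φ(0.30 / (SD × √(2/m))), with m children per large arm. At 50 randomized, m = 20:

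- SD 0.25: z = 0.30/(0.25 × 0.3162) = 3.79, probability 0.9999
- SD 0.30: z = 3.16, probability 0.9992
- SD 0.48: z = 1.98, probability 0.976

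The top of the SD range is a demanding case. A quantity bounded by 0 and 1 with mean 0.65 or 0.35 has SD at most √(0.65 × 0.35) = 0.477. The SD implied by 40 per arm for a comparison of means is much the same: 0.30/(2.802 × √(2/40)) = 0.479.

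**4. All three arms identified.** Simulation of steps 2 and 3 together (40,000 runs), again only if adherence is shown by coded arm:

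| Randomized | 30 points, SD 0.30 | 30 points, SD 0.48 | 15 points, SD 0.48 |
|---|---|---|---|
| 10 | 0.555 | 0.490 | 0.405 |
| 20 | 0.822 | 0.752 | 0.617 |
| 30 | 0.960 | 0.904 | 0.751 |
| 50 | 0.999 | 0.976 | 0.836 |
| 125 | 1.000 | 0.999 | 0.941 |

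**The case against.** The strongest reply is that most of the exposure is conditional and its consequence small.

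- **Timing.** A reader might infer that blinding is lost at the first report. The documents do not support that: they give no accrual by report date, the data to be shown are only proposed at the first DSMB meeting, and at 10 to 20 randomized the codes are not reliably broken.
- **Arms 1 and 3.** A reader might infer that coding hides nothing. The list under Reporting covers accrual, progress, adverse events and data quality and does not name adherence. Adherence is required under Study Monitoring, but in aggregate. If only accrual and safety counts are split by arm, Arm 2 is exposed while Arms 1 and 3 may stay masked.
- **The two parts of Appendix 2.** A reader might infer that the DSMB receives only pooled data, in contradiction of the by-arm report. The text does not say *only*, and aggregate can mean summaries by coded arm. This is an undefined term. Nor can both problems hold for the same data: pooled adherence cannot separate the arms.
- **Who is who.** The study statistician, the project biostatistician and the statistics team are not stated to be the same people.
- **Consequence.** Adherence is recorded by sensor, there is no interim test, and the primary model (GEE with arm, month and their interaction) is largely fixed. Trajectory groups are formed before arm enters, and several later choices have stated criteria, such as BIC, a minimum group size and the Brant test.

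All of this stands as a limit on the claim. It does not remove the core. The by-arm report goes to a statistician, no unblinded statistical role is named, and Arm 2 is exposed by counts that need no adherence data. The DSMB is also asked to advise on efficacy and benefit/risk, which pooled adherence could not inform, so tabulation by coded arm is a natural reading.

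**Conclusion.** The concern holds in a limited form. As written, the plan does not secure the blinding stated in section 7.1.2. Arm 2 is recognisable from arm totals with probability 0.97 at 30 randomized and essentially 1 from 40; this rests only on the ratio and block size.

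Separating Arms 1 and 3 as well depends on adherence being shown by coded arm. In that case all three arms are identified with probability about 0.98 or more at 50 randomized, given the planned 30-point difference and an SD no larger than 0.48. With a true difference of 15 points and SD 0.48, the figure is 0.84 at 50 and 0.94 at 125.

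The documents show no bias in the measurement of adherence and no effect on a stopping decision. What is exposed is the set of analysis choices still open: for the primary outcome the transformation and the month window, and beyond that the secondary and mechanism analyses of trajectories. The point should be fixed, but it does not threaten the trial as a whole.

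**What to change.** 1. In Appendix 2, define aggregate and make Study Monitoring agree with Reporting.
2. Give the PI and the analysing statistician pooled reports only until database lock. Copies that the project biostatistician forwards should be the pooled version.
3. Send by-arm tables (adverse events, asthma admissions and ED visits, adherence) only to the DSMB, as a closed report. They should be prepared by someone already unblinded who does not analyse the trial and, where possible, does not deal with families, so that staff in contact with families do not hold comparative results.
4. Before arm labels are attached, choose one primary month window, settle the transformation, and fix the number and shape of the trajectory groups on pooled data. Name the multinomial or the ordered model in advance, because the proportional-odds check would itself involve arm.
5. If steps 1 to 4 are not taken, section 7.1.2 should no longer claim that the statistics team is blinded.

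The cost is wording in the monitoring plan and the analysis section and, at most, a small reporting role. The downside is that the trial statistician neither sees nor prepares the by-arm DSMB tables.
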